Study Protocol

Official Title: Mechanisms for Alcohol Treatment Change [MATCH] Study

ClinicalTrials.gov ID (NCT number): NCT02918565

Protocol Date: July 2017

Scientific Background

Young adulthood is a developmental period typically associated with escalating alcohol consumption and related risks [1]. Data from the 2019 US National Survey on Drug Use and Health [3] indicate that binge drinking (i.e. heavy episodic drinking), defined as four or more drinks for women and five or more drinks for men over any single occasion [4], increased from 23% at age 18 years to 42% by age 25 years. Immediate risks associated with binge drinking include poor school performance [5], interpersonal violence [6], motor vehicle accidents [7] and poisoning-related death [8].

Evidence-based interventions to reduce hazardous drinking in young adulthood could provide individual and public health benefits. Mobile digital behavioral interventions offer advantages to in-person behavioral interventions in their portability and automation, resulting in lower cost and ease of dissemination [9]. Mobile digital behavioral interventions may be especially useful for young adults, given their high personal ownership and use of smartphones [10]. One especially useful mobile communication modality for delivering behavioral support is text messaging. A recent meta-analysis of alcohol text message trials for young adult hazardous drinkers, including work from our group [11], found that text message interventions reduced self-reported binge drinking [−0.33 episodes per month; 95% confidence interval (CI) = −0.79, 0.12] and weekly alcohol consumption (−18.62 g per week; 95% CI = −39.61, 2.38) [12]. Although effects were small, they represent non-trivial population-level effects.

It remains unknown which behavior change techniques are needed to optimize intervention effectiveness, a critical step to understanding mechanisms of change and informing next-generation text message alcohol interventions [13]. Our group's alcohol text message intervention [11], which was informed by self-regulation theories [14] and the Theory of Planned Behavior [15], used two behavioral change techniques with the largest effect sizes in a meta-analysis of alcohol interventions [16]: self-monitoring and goal commitment, in addition to feedback on drinking behavior, to reduce young adult hazardous drinking. To examine which combination of behavioral change techniques was driving reductions in young adult hazardous drinking, we deconstructed our combined behavioral change techniques intervention (i.e. COMBO) into the following interventions: (1) TRACK (self-monitoring of drinking intentions, desire to get drunk and alcohol consumption) [17]; (2) PLAN (feedback on drinking intentions and desire to get drunk) [18]; (3) USE (feedback on drinking quantity consumed) [19]; and (4) GOAL (prompts to set a personal goal to limit drinking, tips to achieve the goal and feedback on goal success) [20].

Study Objectives

This study used a randomized controlled trial (RCT) design to examine the effects of PLAN, USE, GOAL and COMBO relative to an assessment control arm (i.e. TRACK) on reducing alcohol consumption at 3- and 6-month post-randomization among young adults with hazardous drinking in the emergency department (ED). The primary hypothesis, based on our prior studies [11, 22], was that there would be an ordered effect of the intervention in reducing the number of binge drinking days at 3-month post-randomization. That is, compared with the TRACK, (1) the combination of behavioral change techniques (i.e. COMBO) would show the greatest reductions in past month binge drinking days at 3-month follow-up and (2) component behavioral change

techniques (i.e. PLAN, USE and GOAL) would show intermediate reductions in past month binge drinking days at 3-month follow-up. We did not compare the four active conditions against each other. We explored intervention effects on secondary outcomes of binge drinking prevalence, drinks per drinking day and past month number of negative drinking consequences at 3- and 6-month follow-ups.

Study Design & Methods

The study was a parallel five-group individually randomized clinical trial that compared the efficacy of 12-week interventions utilizing different behavioral change techniques on reducing binge drinking at 3- and 6-month post-randomization among young adults with hazardous drinking. Assessor-blinded self-reported outcomes at 3 and 6 months were examined. The study was funded by the National Institute on Alcohol Abuse and Alcoholism (NIAAA). The study protocol was approved by the University of Pittsburgh Human Research Protection Office.

Participants who completed the baseline assessment were instructed to text a study telephone number within 24 hours. Only individuals whose telephone numbers matched the telephone numbers provided during the enrollment process were eligible. Once this match was recognized, participants received several texts welcoming them to the study and describing the 2-week run-in prior to randomization. During the 2-week run-in following the ED enrollment, on the 2 days in the week when participants typically drank alcohol (based on self-report data collected at baseline), subjects were prompted at 3 p.m. to report drinking plans and desire to get drunk, without receiving any directive feedback. This design feature of delivering messages on days when subjects typically drank was intended to ensure that we efficiently captured reports of drinking on days when it typically occurred. If no response was received within 2 hours, each text query was repeated once, and the response window closed after an additional 2 hours if no response was received. Only individuals who responded to at least 50% of the text queries and responded that they wished to continue participation with 'GO' at the end of the 2-week run-in were randomized to one of the five conditions. Randomization was performed by the software sequentially selecting a condition assignment in blocks of 10 from a randomization list generated a priori and concealed from participants and research staff throughout the trial.

The interventions were all delivered via an automated text messaging intervention for 12 weeks using software run by the Office of Academic Computing at the University of Pittsburgh Medical Center. We chose text messaging, given its ubiquity and preferential role for communication among young adults [17] as well as its proven effectiveness to deliver other health support [18]. Each intervention arm was designed to focus upon a unique component or combination of behavioral change techniques, as shown in Supporting information, Table S1 and as described in prior work [3]. The TRACK arm was intended to promote self-monitoring [17] of plans to drink, desire to get drunk and alcohol consumption and was identical to the run-in messaging. The PLAN arm was intended to challenge drinking expectancies [18] by providing feedback on drinking plans and desire to get drunk in addition to promoting self-monitoring. The USE arm was intended to modify post-drinking appraisals [19] by providing feedback on reported number of drinks consumed after their typical drinking day. The GOAL arm provided self-regulation support to limit alcohol consumption [20] by prompting drinking limit goal commitment [25], providing feedback on goal self-efficacy [26] and providing feedback on goal success to either bolster future goal striving [27] or reframe goal failure [28]. The COMBO arm combined all of the above behavioral change techniques [3].

Primary outcome

The primary outcome was the number of past month binge drinking days at 3-months post-randomization calculated from a 30-day time-line follow-back (TLFB) calendar [39]. Participants completed a web-based calendar and a visual reference displaying standard drink amounts and were asked to report their alcohol consumption by day. A standard drink was defined as 12 oz. of beer, 5 oz. of 12% table wine, 12 oz. of wine cooler or 1.25 oz. of 80-proof liquor. We calculated the number of days when a woman reported four or more standard drinks or a man reported five or more standard drinks as a binge drinking day.

Secondary outcomes

Secondary outcomes included number of binge drinking days at 6 months as well as drinks per drinking day and prevalence of any binge drinking at 3 and 6 months, all derived from the 30-day TLFB. We calculated drinks per drinking day as the mean drinks divided by the number of days with any alcohol consumption. We calculated the prevalence of any binge drinking days in the past 30 days, represented as a dichotomous variable (1 = any binge drinking day; 0 = no binge drinking day). Secondary outcomes also included alcohol-related consequences from the Brief Young Adult Alcohol Consequences Questionnaire (B-YAACQ) [40]. The B-YAACQ is a 24-item measure of alcohol-related problems that utilizes a dichotomous (present or absent) scoring format. Higher scores (count of items marked as 'present') on the B-YAACQ not only indicate a wider variety but also reflect a more severe pattern of alcohol-related problems.

Eligibility Criteria

Patients aged 18–25 years who presented to one of four EDs in western Pennsylvania were eligible to be screened if they were medically stable, provided permission to be approached and were not being discharged imminently. Patients were excluded from screening in the ED if they were already enrolled into the trial or were not interested in study participation. Screened patients were included if they reported an Alcohol Use Disorder Identification Test for Consumption (AUDIT-C) score of ≥ 3 for women or ≥ 4 for men [23]. We used the AUDIT-C to screen-in patients as it is a brief alcohol screening instrument that reliably identifies people who are hazardous drinkers or have active alcohol use disorders (including alcohol abuse or dependence) [24] and permits comparison to prior studies [11]. Screened patients were excluded if they reported not being interested in participating in a clinical trial, past treatment for drug or alcohol problems, current psychiatric treatment or did not own their own telephone with text messaging.

Statistical Considerations

Missing outcomes (primary and secondary)

For intent-to-treat (ITT) analyses, following current recommendations when outcomes are missing [41, 42] and following best practices for alcohol trials [43], we used multiple imputation procedures to generate accurate estimates of uncertainty. We first ensured that missing outcome data were not missing completely at random (MCAR) using Little's test [44]. We therefore assumed that outcomes were missing at random (MAR) [45]. To reduce probability of

outcomes being missing due to unmeasured factors (i.e. missing not at random: MNAR), we examined baseline covariates associated with missing outcomes (see Supporting information, Table [S3](#)) and included those with significant associations in the imputation model. Because the pattern of missingness was non-monotonic, we used multiple imputation chained equations (MICE) [\[46\]](#). Because missing binge drinking days were not normally distributed and bounded by 0 to 30 day, we used predictive mean matching with $k = 5$ nearest neighbors [\[47\]](#). We included sex, college-enrolled, tobacco use and baseline impulsivity score as predictors of outcomes. We generated 30 sets of imputed data based on the highest fraction of missing information, which was 0.27, as per recommendations [\[48\]](#). We checked how well the imputation model fitted the observed outcome data by inspecting their distributions in each treatment arm.

Analytical models

For our primary outcome analysis of mean binge drinking days at 3-month follow-up as well as the secondary outcome analysis of mean binge drinking days at 6-month follow-up, we used separate negative binomial regression functions [\[49\]](#). Secondary outcome analyses also included at 3- and 6-month mean drinks per drinking day using the Poisson regression function, the point prevalence of any binge drinking days in the past month using the logit function and mean number of negative alcohol consequences (B-YAACQ) using a negative binomial regression. Covariates with significant univariate associations with the primary and secondary outcomes were included in the models as covariates, and white race, baseline tobacco use, baseline impulsivity score and baseline measures of the main outcome (e.g. binge drinking days) were kept in the final models, as their inclusion improved model fits (based on Akaike information criterion and Bayes information criterion). Interactions between intervention arm and site of recruitment were examined, and no significant interactions were identified in relation to the primary or secondary outcomes. Estimated treatment effects are reported as either adjusted β or odds ratios (ORs) with 95% CIs. Sensitivity of all imputed model findings was assessed by conducting complete case analyses (CCA).

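### The formula given for drinks per drinking day is not drinks per drinking day as worded; correct the sentence and check the scoring code

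*Combined protocol and SAP*

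**What the plan says.** The Secondary outcomes section lists "drinks per drinking day and prevalence of any binge drinking at 3 and 6 months, all derived from the 30-day TLFB". It then gives the scoring rule: "We calculated drinks per drinking day as the mean drinks divided by the number of days with any alcohol consumption". This is the only formula for the outcome in the document.

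Three other places bear on it:

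- Primary outcome section: on the web-based calendar, participants "were asked to report their alcohol consumption by day". Total drinks and the count of drinking days are therefore both available for anyone who completed it.
- Analytical models: the outcome is analysed as "3- and 6-month mean drinks per drinking day using the Poisson regression function". This repeats the name and gives no formula.
- Study Objectives: the outcome's role is exploratory ("We explored intervention effects on secondary outcomes of binge drinking prevalence, drinks per drinking day and past month number of negative drinking consequences").

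**The concern.** Drinks per drinking day measures intensity: how much a person drinks on a day when they drink. It needs total drinks on top and drinking days underneath. The stated rule has the right denominator but puts a mean on top, so an average is averaged again. No other section supplies a different numerator.

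Two things are at stake if an analyst programs the sentence as it stands. On one reading the score falls as a person drinks on more days at the same intensity, so an arm that reduced drinking days without changing intensity would look worse. On the other reading the score is on the wrong scale. That matters for a Poisson model, whose assumed variance equals the mean and so depends on the units.

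**Working it through.** The plan states no numerical value for this outcome, so there is no figure to reproduce. The check compares the named quantity with the literal formula.

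**Notation.** T = total standard drinks over 30 days; d = days with any drinking. Both come from the daily calendar.

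- Named quantity: T/d.
- Reading 1, mean per drinking day: (T/d)/d = T/d². This equals T/d only when d = 1.
- Reading 2, mean per calendar day: (T/30)/d = (T/d)/30. This is 1/30 of the named quantity for everyone.

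**Illustrative participants** (invented values, not trial data):

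| Drinking days d | Drinks on each | T | T/d | Reading 1 | Reading 2 |
|---|---|---|---|---|---|
| 4 | 8 | 32 | 8.0 | 32/16 = 2.0 | 32/120 = 0.267 |
| 20 | 8 | 160 | 8.0 | 160/400 = 0.4 | 160/600 = 0.267 |
| 8 | 5 | 40 | 5.0 | 40/64 = 0.625 | 40/240 = 0.167 |
| 12 | 7 | 84 | 7.0 | 84/144 = 0.583 | 84/360 = 0.233 |
| 4 | 3 | 12 | 3.0 | 12/16 = 0.75 | 12/120 = 0.100 |

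The first two rows have equal intensity, but reading 1 separates them by 2.0/0.4 = 5-fold. In the last two rows reading 1 reverses the order: true values of 7.0 and 3.0 become 0.583 and 0.75. Reading 2 keeps every ordering and ratio.

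**Effect on the Poisson model.** With a log link, multiplying the outcome by a constant c shifts the intercept by log c and leaves the arm coefficient unchanged. The model-based information is proportional to the fitted mean, so the model-based standard error is multiplied by 1/√c. With c = 1/30 the factor is √30 = 5.48. A robust (sandwich) standard error does not change under constant rescaling. The factor compares the same model on two scales; it does not say that the model-based error on the T/d scale is itself correct.

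**Simulation.** All inputs are assumptions: 1,000 participants per arm, about 5 drinks per drinking day, and about 5 to 8 drinking days.

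- Equal intensity, fewer drinking days in one arm (about 5 against 8): the log ratio for T/d was 0.001. Under reading 1 it became +0.53, a ratio of exp(0.53) ≈ 1.70 against the arm with fewer drinking days.
- Lower intensity in one arm (4.5 against 5), same drinking days: the log ratio was −0.106 for both T/d and reading 2. The model-based standard error was 0.0205 for T/d and 0.1124 for reading 2; 0.1124/0.0205 = 5.48, as the algebra predicts.

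**The case against.** The strongest reply is that the intended measure is not in doubt. The outcome's name states it, the Analytical models section calls it a mean number of drinks per drinking day, the denominator in the formula is the right one, and the daily data needed are collected. The likeliest explanation is a misplaced word: the mean is the result of the division, not its numerator. Reading 1, which carries the worst consequences, is the less plausible one, because it requires an analyst to compute the outcome correctly and then divide it by drinking days again. Most of this stands, and it is why the point is not a serious one. It does not make the sentence right: a regression needs a defined score for each participant, and this is the only rule given for producing it.

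A reader might infer three stronger things that the documents do not support.

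- That the 3- and 6-month scores are wrong. The documents contain no scores, group means or code for this outcome, so nothing shows that the literal formula was used.
- That the standard errors are inflated 5.5-fold. This needs both reading 2 and model-based errors, and the Analytical models section does not say whether model-based or robust errors were used.
- That the error also enters the models through a baseline covariate. That section says baseline values of the main outcome were kept and gives binge drinking days as its example. Whether baseline drinks per drinking day entered any model, and how it was scored, is not stated.

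**Conclusion.** The definition is wrong as worded, and this follows from algebra alone: neither participant-level reading gives T/d, apart from the trivial case d = 1 under reading 1. What it did to the analysis is unknown. If the sentence is a slip and the code used total drinks, there is no numerical effect. If reading 2 was coded, arm ratios hold, scores are 30 times too small, and model-based standard errors are about 5.5 times those on the T/d scale. If reading 1 was coded, the outcome no longer measures intensity and an arm comparison could change direction.

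The reach is limited to one exploratory secondary outcome at two time points, with its baseline value as a conditional addition. Binge drinking days at either time point, any-binge prevalence and the B-YAACQ count do not use this formula. Severity is minor to moderate.

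**What to change.** Reword the rule so that the score is the total standard drinks recorded across the 30-day calendar, divided by the count of days on which any drinking was recorded. Then check the scoring code against it, including any baseline version of the variable. If the code already uses the total, correcting the text is enough. If the literal formula was programmed, recompute the 3- and 6-month scores (and the baseline score, if used), re-impute this outcome, and re-run its models.

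The same edit is a convenient place to settle a separate gap: no rule covers a participant with no drinking days, for whom the ratio is 0/0. Stating whether the Poisson standard errors are model-based or robust would also help.

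The cost is one sentence and a code check and, at most, a re-run of one derived variable from daily data that the plan already collects. No new data are needed.

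### Rejecting MCAR does not justify MAR, and complete-case analysis, the only stated sensitivity analysis, is a weak check on dropout that depends on unseen drinking differently by arm; an arm-specific delta analysis would fill the gap

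*Combined protocol and SAP*

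**What the plan says.** Under Statistical Considerations, the part on missing outcomes reports that Little's test ruled out MCAR and continues: "We therefore assumed that outcomes were missing at random (MAR"). It names MNAR as a concern and responds by screening baseline covariates for association with missingness and putting the significant ones in the imputation model. On predictors it says: "We included sex, college-enrolled, tobacco use and baseline impulsivity score as predictors of outcomes". Imputation is by chained equations with predictive mean matching (5 neighbours) and 30 imputed datasets, chosen from a highest fraction of missing information of 0.27. The stated diagnostic is: "We checked how well the imputation model fitted the observed outcome data by inspecting their distributions in each treatment arm".

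The part on analytical models uses negative binomial regression for binge days and says that "baseline measures of the main outcome (e.g. binge drinking days) were kept in the final models". On sensitivity it says only: "Sensitivity of all imputed model findings was assessed by conducting complete case analyses (CCA"). The supplied text describes no delta-adjusted, pattern-mixture, reference-based or other MNAR analysis.

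**The concern.** The word linking the two steps makes MAR read as a consequence of the test. Little's test addresses MCAR only. Once MCAR is rejected, missingness may depend on measured data alone (MAR) or also on the unseen outcome (MNAR), and nothing in the observed data tells these apart. Adding baseline predictors of missingness makes MAR more plausible but does not assess departures from it. The distribution check compares with observed outcomes, so it does not reach the unseen ones.

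Complete-case analysis (CCA) does not close the gap. Covariate-adjusted CCA and multiple imputation (MI) under MAR both rely on missingness not depending on the unseen outcome given the data used. If heavier drinkers drop out more in one arm than in another, both can move the same way by about the same amount. The outcome is self-reported drinking and the arms receive different feedback, so such a mechanism is possible. At stake is how far the four contrasts with TRACK on 3-month binge days can be called robust to missing data.

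**Working it through.** **Figure in the plan.** The missing-data section offers one figure to check: 30 imputations for a fraction of missing information of 0.27. A common rule is at least 100 × 0.27 = 27, which 30 meets. Relative efficiency is 1/(1 + 0.27/30) = 0.991. The plan does not state its rule, so this is a consistency check only. The number of imputations is adequate, and the point does not depend on it.

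**Shift needed to offset a yardstick effect.** Let a share p be missing in each arm, and let the unseen values differ from their MAR imputations by d1 days (active) and d0 days (TRACK). The mean difference moves by p × (d1 − d0). With d0 = 0, an effect E is cancelled at d1 = |E|/p. The yardstick is E = 0.33 episodes per month, the meta-analysis estimate in Scientific Background. Its interval includes zero and it is not this trial's design effect. The shares p are assumed, because the documents give none:
- p = 15%: 0.33/0.15 = 2.20 days
- p = 27%: 0.33/0.27 = 1.22 days
- p = 35%: 0.33/0.35 = 0.94 days

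An equal shift in both arms with equal missingness moves the difference by p × 0 = 0.

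**Simulation on the rate-ratio scale (all inputs assumed).** 1000 trials per scenario; 150 per arm; negative binomial outcome with mean 2.7 days and dispersion 1; baseline mean 3.5 days; baseline-outcome correlation 0.5; missingness rising by 0.1 log-odds per binge day; 30 imputations by predictive mean matching (k = 5) using arm and baseline drinking; negative binomial model adjusted for baseline drinking. Factor = estimated rate ratio / full-data rate ratio; Monte Carlo SE at most 0.0033.

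| Scenario | CCA | MI |
|---|---|---|
| Equal mechanism, 27% / 27% missing | 1.001 | 1.002 |
| Common mechanism, 30% / 20% missing | 0.973 | 0.973 |
| Active arm only, 15 / 27 / 35% | 0.953 / 0.925 / 0.904 | 0.950 / 0.919 / 0.896 |
| TRACK only, 15 / 27 / 35% | 1.051 / 1.082 / 1.104 | 1.053 / 1.090 / 1.114 |

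The baseline correlation matters. For active-only dependence, MI gave 0.938 / 0.901 / 0.882 at correlation 0.3 and 0.972 / 0.946 / 0.933 at 0.74. In the active-only rows the mean absolute CCA-MI gap within a trial was 0.012 / 0.020 / 0.024 on the log scale, smaller than the bias itself (for example ln 0.919 = −0.084).

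**A second simulation under other assumptions.** 180 per arm, no true effect, dependence in the active arm only at 0.2 log-odds per binge day, 22% vs 23% missing, 200 trials. The full-data rate ratio was 0.995, CCA 0.914 and MI 0.907. The mean absolute CCA-MI log difference was 0.011, against 0.009 without outcome dependence, so the comparison barely registered the bias. Rejection rates were 10% (CCA) and 12.5% (MI), against 3.5% and 5.0% (Monte Carlo SE about 2 points). Near-equal missing rates did not rule out the problem.

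**Does a delta analysis respond?** In the first simulation (active-only, 15 / 27 / 35%), shifting imputed values by +0.5 day in the active arm gave 0.982 / 0.977 / 0.972, and +1 day gave 1.014 / 1.035 / 1.046, so the two bracket 1.00. A shift of +1 in both arms gave 0.951 / 0.924 / 0.907, almost no correction. The shift therefore has to differ by arm. Because values are cut at 0, a −1 shift achieved only −0.72 to −0.74.

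**The case against.** The text calls MAR an assumption, names MNAR and takes a sensible step to limit it. A fair reading is that MCAR was rejected and MI under MAR was therefore used. No imputation model or fit check can test MAR, so failing to do so is not a fault. That stands: the criticism comes down to one loose inference and one absent supplementary analysis.

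The magnitudes are hypothetical. Factors beyond about 3% arise only when dependence acts in one arm. The assumed strength implies a missing-minus-observed gap of 1.0-1.2 days on a mean of 2.7, roughly 40%. The run-in, which required replies to at least half of the text queries, also lowers the risk in every arm, though it does not remove it. This stands too.

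The simulations above impute without 6-month data. The plan reports a non-monotonic pattern and chained equations, so the two waves may have been imputed together; the text does not confirm it. With a 6-month outcome added (27% missing, active-only, 250 trials, 8 imputations), the MI factor moved from 0.919 to 0.928, from 0.917 to 0.931, and in the most favourable case (3-to-6-month correlation 0.82, 60% of non-responders seen at 6 months) from 0.915 to 0.948. About 12-40% of the log bias went. In that last case the average MI-CCA log gap reached 0.027, so the comparison can carry some signal. Bias remained throughout, but the figures in the table are upper-end if imputation was joint.

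A reader might infer that the trial's results are biased by dropout, or that the authors claim robustness because CCA and MI agreed. The documents support neither: they report no differential dropout and no such agreement, only that sensitivity was assessed. Nor does rejecting MCAR make MNAR as likely as MAR; it leaves both possible.

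**Conclusion.** The point holds as an untested risk. MAR does not follow from Little's test, and agreement between CCA and MI, if found, would be weak evidence against arm-specific, outcome-dependent dropout. The size in this trial is unknown. Under assumed inputs it runs from no bias (equal mechanism and rates), through a factor of about 0.97 (common mechanism, 30% vs 20% missing), to 0.90-0.95 or 1.05-1.11 when dependence is confined to one arm. As an example of the last, a true rate ratio of 0.80 with TRACK-only dependence at 27% missing and a factor of 1.08 would appear as about 0.80 × 1.08 = 0.86. The bias can thus hide a benefit as well as create one.

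These figures rest on assumed arm sizes, missing shares, strength of dependence and baseline correlation. The 0.27 in the plan is a fraction of missing information and should not be read as a missing rate. Supporting Table S3 was not available, so it may hold relevant detail. This is a cheap improvement that should be made; confidence is medium.

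**What to change.** Keep MI under MAR as the primary analysis and CCA as supplementary. Describe MAR as an untestable working assumption, not as a consequence of Little's test.

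1. Confirm that arm and baseline binge days were in the imputation model. The listed predictors name neither, though the list may not be exhaustive. Re-run the imputation if either was left out; otherwise a zero shift is not a sound arm-specific MAR reference.
2. Add a delta-adjusted MI analysis of 3-month binge days. Use separate shifts for each active arm and for TRACK, in both directions and including zero, with values kept within 0-30 days. Write down a plausibility limit before the shifted results are viewed.
3. Report the tipping point for each of the four contrasts with TRACK, the achieved mean shifts after truncation, and missing rates by arm.
4. Label the analysis post hoc if results are already known. The text suggests they are, since it reports for example that "no significant interactions were identified in relation to the primary or secondary outcomes" (for arm by recruitment site).

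Text-message reports are optional auxiliary variables. For the run-in, first confirm what was collected: Study Design & Methods says "subjects were prompted at 3 p.m. to report drinking plans and desire to get drunk, without receiving any directive feedback", while its account of TRACK covers "plans to drink, desire to get drunk and alcohol consumption and was identical to the run-in messaging". Post-randomization reports should be used only with imputation by arm or with arm interactions.

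Cost: one added analysis on the existing 30 datasets if step 1 is satisfied, plus a paragraph and a small table; a new imputation if step 1 fails or text reports are added. Conclusions may look less certain, and a post hoc check carries less weight than a planned one.

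### The imputation model names only baseline predictors and no measure of text engagement after randomisation, although every arm exchanges texts for 12 weeks

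*Combined protocol and SAP*

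**What the plan says.** All references are to the combined protocol and SAP.

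- **Missing outcomes (primary and secondary).** Outcomes are assumed missing at random. To lower the chance that loss is driven by unmeasured factors, the plan says "we examined baseline covariates associated with missing outcomes" and "included those with significant associations in the imputation model". It then states: "We included sex, college-enrolled, tobacco use and baseline impulsivity score as predictors of outcomes". The method is chained equations, chosen because missingness is non-monotonic, and for binge drinking days "we used predictive mean matching with $k = 5$ nearest neighbors". There are 30 imputed sets, based on a highest fraction of missing information of 0.27.
- **Study Design & Methods.** All interventions run by automated text for 12 weeks, roughly to the 3-month primary endpoint. TRACK covers self-monitoring of plans, desire to get drunk and consumption. USE works by "providing feedback on reported number of drinks consumed after their typical drinking day". For the run-in, an unanswered query is repeated, and "the response window closed after an additional 2 hours if no response was received". Randomisation requires replies to at least 50% of run-in queries.
- **Analytical models.** The only sensitivity analysis for missing data is a complete-case analysis.

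**The concern.** Missing at random is a statement conditional on what is in the imputation model. In a text-delivered alcohol trial, disengagement and drinking after randomisation are plausible causes of a missing 3-month outcome, and the trial's own system observes at least the first of these. The plan already treats reply rate as a marker of engagement when deciding who is randomised, but names no such variable when modelling who is lost.

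Predictive mean matching copies an observed value from someone with a similar prediction. If the predictions rest on baseline variables alone, a participant who stopped replying can receive a value from a fully engaged participant with a similar baseline. If the link between disengagement, drinking and loss differs between an active arm and TRACK, the contrast shifts. The complete-case analysis cannot reveal this, because it also ignores the text data.

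**Working it through.** **The plan's own figure.** With m = 30 and a fraction of missing information of 0.27, relative efficiency is 1/(1 + 0.27/30) = 0.991. The number of imputations is adequate, but more imputations do not cure bias from an omitted predictor. The document gives no sample size and no missingness by arm, so every input below is an assumption.

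**Bias on a standardised scale.** Let a be a text-based auxiliary (standard normal), u the outcome residual after arm and baseline outcome (assumed to be in the imputation model already), and r their correlation. Each arm has 30% missing, with logit slope s on a. Imputation without a leaves an arm's mean biased by

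bias = r × E[a | observed].

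With 2 million simulated people, E[a | observed] is −0.142 for s = 0.5 and −0.251 for s = 1.0. So:

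| r | s = 0.5 | s = 1.0 |
|---|---|---|
| 0.3 | −0.043 | −0.075 |
| 0.5 | −0.071 | −0.126 |
| 0.6 | −0.085 | −0.151 |

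- *Equal slopes in both arms:* the two biases cancel and the contrast bias is about 0.
- *Slope in one arm only:* the contrast is biased by 0.04 to 0.15 residual SD. The sign depends on which arm has the slope and on whether heavier or lighter drinkers are lost.
- *Equal slopes, auxiliary used in one arm only:* that arm is corrected and the other is not, so a bias of 0.04 to 0.15 SD appears where there was none.

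**Bias in binge drinking days.** A second simulation used predictive mean matching (k = 5), 300 per arm, 5 imputations, 150 replicates, 23 to 28% missing and a true contrast of about −0.33 days. Baseline and arm were in both imputation models. The text variable was fully observed, and its correlation with post-randomisation drinking was varied. The Monte Carlo standard error of the baseline-only bias was 0.012 to 0.016.

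| Correlation | Slopes TRACK / active | Bias, baseline only | Bias, text variable added |
|---|---|---|---|
| 0.5 to 1.0 | equal (0/0 or 0.7/0.7) | −0.01 to +0.02 | −0.04 to 0.00 |
| 0.5 | 0.2/1.0; 0/1.2 | −0.14; −0.21 | −0.06; −0.03 |
| 0.8 | 0.2/1.0; 0/1.2 | −0.25; −0.35 | −0.07; −0.07 |
| 1.0 | 0.2/1.0; 0/1.2 | −0.30; −0.44 | −0.10; −0.12 |

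As a yardstick, the meta-analysis in Scientific Background gives −0.33 episodes per month. Under differential loss the bias can be of that order, and the auxiliary reduces it without removing it.

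**Precision.** With non-differential loss, the ratio of variance with the auxiliary to variance without it is [(1 − r²)/(1 − p) + r²] × (1 − p) = 1 − r²p. Taking p = 0.27, the reductions are 0.09 × 0.27 = 2.4%, 0.25 × 0.27 = 6.8% and 0.36 × 0.27 = 9.7%. This treats the fraction of missing information as a proportion missing, which it is not, and 0.27 is the highest value reported. The figures are therefore a rough ceiling.

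**The case against.** The case for leaving the plan alone has several good parts.

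- **A reader might infer that everyone lost is imputed from baseline data alone.** The document does not establish this. The section covers primary and secondary outcomes together and uses chained equations for a non-monotonic pattern, so an observed 6-month outcome may inform a missing 3-month one, and vice versa. The point is secure only for people who miss both visits.
- **The full predictor list cannot be seen.** The screen is reported in Table S3, which is not in the document. Run-in reply rate precedes randomisation and could be among the covariates screened.
- **A reader might infer that dated drink counts are held for everyone.** That is inference. The response window is described for the run-in only, and the run-in text mentions plans and desire, not drinks. Nothing says outright that PLAN and GOAL collect drink counts, and Table S1, which sets out arm content, is not in the document.
- **Silence by text is not the same as a missing outcome.** Outcomes come from a web-based calendar, and the 50% run-in rule narrows the range of engagement.
- **A reader might infer that the trial's contrast is biased towards the active arms.** Nothing in the document supports this. The negative signs in the tables follow from assuming that heavier drinkers are lost mainly from the active arm.

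All of this stands, and it limits the claim. It does not supply a reason to leave engagement after randomisation out of a model whose stated aim is to reduce dependence on unmeasured factors.

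**Conclusion.** The point holds in a limited form. The screen is restricted to baseline covariates, every named imputation predictor is measured at baseline, and no engagement variable from the 12 weeks of texting is named. For people who miss both follow-ups, the imputation as documented ignores what they did after randomisation. Nothing in the section is contradictory or invalid. It is a gap measured against the plan's own aim, and cheap to close.

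The effect on the contrast ranges from about 0 (missingness depends on engagement equally in the arms compared) to 0.04 to 0.15 residual SD in either direction (dependence in one arm only). This rests on assumed values: 30% missing, auxiliary correlation 0.3 to 0.6 and logit slope 0.5 to 1.0. It would be wrong to conclude that the auxiliary removes the bias. It does so on the standardised scale only because there it is fully observed and the sole cause of loss.

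**What to change.** In Missing outcomes (primary and secondary), extend both the missingness screen and the chained-equations model, fitted by arm, to text variables recorded in the same way in all five arms:

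- proportion of texts answered in weeks 1–4, 5–8 and 9–12;
- week of last reply or opt-out;
- run-in reply rate, if not already screened.

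Use text-reported plans, desire to get drunk or drinks only if they were collected in every arm. Adding them where available is tempting, but an auxiliary present in some arms only can itself bias the contrast by as much as the omission could. Keep all these variables out of the outcome models in Analytical models, since they are measured after randomisation. Report the result beside the current imputation, labelled as added after the fact.

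The cost is data preparation and a re-run of the imputation, with no new data collection, visits or participants, provided the reply records were kept as the automated system suggests. The main downside is that text variables become sparse once a person goes silent, so they must be summarised by period and will carry limited information late in follow-up.
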